1.3.3 Phase I Dose-Finding and Pharmacokinetics

A total of 55 patients were enrolled in the dose escalation phase of study PLX06-02, including patients with metastatic melanoma (n=50), thyroid cancer (n=3), rectal carcinoma (n=1) and ovarian cancer (n=1). Several different capsule strengths and formulations were evaluated in this part of the study. Twenty-six patients received doses of vemurafenib ranging from 160 mg to 1120 mg b.i.d using the optimized drug formulation (referred to as micro-precipitated bulk powder [MBP] formulation) with greater bioavailability. With this optimized formulation, minimum efficacious exposures above the exposure identified in the preclinical models ($\geq 400\mu\text{M}\cdot\text{h}$) were achieved at 240 mg b.i.d. Vemurafenib MBP formulation has shown dose proportional increases in exposure across all cohorts, particularly from 240 to 960 mg b.i.d. Mean steady state exposure levels of vemurafenib (area under the plasma concentration-time curve, AUC_{0-24h}) in these dose cohorts ranged from 467.1 $\mu\text{M}\cdot\text{h}$ to 1324.6 $\mu\text{M}\cdot\text{h}$. The 960 mg b.i.d dose of vemurafenib achieved mean steady state exposure levels of 69.6 μM and 1324.6 $\mu\text{M}\cdot\text{h}$, for maximum plasma concentration (C_{max}) and AUC_{0-24h}, respectively.

An apparent mean half-life of ~90 hours (range, 30 to 145 hours) following multiple doses in patients receiving 960 mg bid in the melanoma extension cohort was determined based on the mean accumulation ratio of vemurafenib exposure between Day 1 and Day 15. With the twice-daily dosing regimen, all patients were exposed to relatively constant daily levels of the drug at steady state.

Dose-limiting toxic effects were not observed until a dose of 720 mg b.i.d. At the next highest dose given to one group of patients, 1120 mg b.i.d, four of six patients developed non-life threatening dose-limiting toxicity (DLT): three patients with Grade 3 rash (two of whom also had Grade 3 fatigue) and one patient with Grade 3 arthralgia. All events resolved with temporary drug interruption. In all cases, patients resumed treatment at lower doses of 720 mg b.i.d. One DLT, Grade 4 pancytopenia, was observed at 720 mg b.i.d. Upon resolution of the pancytopenia after 9 days of study drug interruption, the patient was rechallenged with vemurafenib at a lower dose of 360 mg b.i.d without recurrence of the pancytopenia. No new

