1.3.5.4 Cardiac effects in NP2265/BRIM-2

The effects of single and multiple doses of vemurafenib 960 mg bid on ECG measurement, including the QT interval, were evaluated in 132 adult patients with metastatic melanoma in the phase 2 study, NP22657. Centralized measurement of ECG intervals and T/U wave morphology was conducted by the core ECG laboratory on the robust schedule of serial time matched 12-lead ECGs obtained for up to 16 cycles. For each of the time points, the means from the available triplicate assessments were used as a single observation for the numeric ECG parameter. The T-wave and U-wave morphology and the ECG normality were assessed on each ECG from a triplicate.

Vemurafenib treatment at 960 mg bid did not appear to have a clinically meaningful effect on heart rate (HR). The study population-specific correction (QTcP) had eliminated most of the bias from the QT-RR relationship and was therefore used for the primary statistical analyses of variables related to the QTc interval.

Ninety-one patients (68.9%) exhibited normal ECG values (n=25) or developed new abnormal yet clinically insignificant ECG changes (n = 66). However, 41 patients (31.1%) exhibited new ECG changes considered to be abnormal and potentially significant. No patients developed new abnormal U waves, and 19 patients (14.4%) had new abnormal T-waves. Vemurafenib did not

cause a meaningful change from the time-matched baseline in either the QRS or the PR (PQ) interval.

Two patients (1.5%) developed treatment-emergent absolute QTcP values > 500 ms (CTC Grade 3), while 49 (37.1%) and 6 (4.5%) patients exhibited QTcP values > 450 ms and > 480 ms, respectively. No patients had treatment-emergent QT (uncorrected) values > 500 ms. Maximum treatment-emergent individual QTcP changes from baseline of > 30 ms were observed in 58 (43.9%) of patients, but only one patient (0.8%) exhibited a QTcP change from baseline of > 60 ms.

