4.3 EXCLUSION CRITERIA

Exclusion Criteria:

1. Melanoma, papillary thyroid cancer or haematological malignancies (with the exception of multiple myeloma).
2. Uncontrolled concurrent malignancy (early stage or chronic disease is allowed if not requiring active therapy or intervention and is under control)
3. For MM, solitary bone or solitary extramedullary plasmacytoma as the only evidence of plasma cell dyscrasia
4. Active or untreated CNS metastases.
 - Patients with brain metastasis are eligible if asymptomatic, off corticosteroid therapy, and without evidence of disease progression in brain for \geq 2 months.
 - Patients with incidentally found brain metastases that are asymptomatic and for which no treatment is planned are also eligible.
5. History of or known carcinomatous meningitis

6. Concurrent administration of any anti-cancer therapies (e.g., chemotherapy, other targeted therapy, experimental drug, etc.) other than those administered in this study
7. Known hypersensitivity to vemurafenib or another BRAF inhibitor. In addition, for Cohort 3b only: known hypersensitivity to cetuximab
8. Prior treatment with a BRAF or MEK inhibitor (prior sorafenib is allowed)
9. Pregnant or lactating women
10. Refractory nausea and vomiting, malabsorption, external biliary shunt or significant bowel resection that would preclude adequate absorption.
11. Any of the following within the 6 months prior to first vemurafenib administration:
 - Myocardial infarction, severe/unstable angina, symptomatic congestive heart failure, cerebrovascular accident or transient ischemic attack
12. Pulmonary embolism within 30 days prior to first study medication administration
13. Hypertension not adequately controlled by current medications within 30 days prior to first study medication administration
14. History or presence of clinically significant ventricular or atrial dysrhythmias \geq Grade 2 (National Cancer Institute Common Terminology Criteria for Adverse Events, Version 4.0 [NCI CTCAE, v4.0])
15. Corrected QT (QTc) interval \geq 450 msec at baseline or history of congenital long QT syndrome or uncorrectable electrolyte abnormalities
16. Uncontrolled medical illness (such as infection requiring treatment with intravenous [IV] antibiotics)

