b. Treatment interruptions or and/or dose reductions for Grade 3 haematology test abnormalities, except for neutropenia and thrombocytopenia, will be at investigator's discretion.

c. Discontinue permanently if starting dose is 480 mg b.i.d.

Prolongation of the corrected QT (QTc) interval (change from baseline) was observed in a substudy of the NP22657/BRIM-2 phase II trial. As a result of these findings, the following recommendations have been developed to minimize the risk of ventricular arrhythmia in patients with metastatic melanoma treated with vemurafenib:

Avoid combination with other agents with known potential to lead to prolongation of QTc interval, if possible.

ECG monitoring, with a focus on QTc interval, should occur during the Screening/Baseline period, 28 days after starting vemurafenib, every 28 days for the following 3 months, and every 12 weeks thereafter until study drug discontinuation at the End of Treatment Visit, and at the Safety Follow-Up Visit.

If QTc interval exceeds 500 ms or the change from baseline is > 60 ms, vemurafenib treatment should be temporarily interrupted. The Investigator should check electrolytes (K+, Mg++, and Ca++) with a focus on hypokalaemia, correct any electrolyte abnormalities prior to reinstitution of therapy, recheck concomitant medications to insure that none has been implicated in QTc prolongation, and rule out or control other cardiac risk factors (i.e., ischemia). ECG should be monitored weekly until QTc decreases to less than 500 ms, at which point treatment should be reinitiated at one reduced dose level, i.e., from 960 mg b.i.d. to 720 mg b.i.d. If a subsequent increase in QTc to > 500 ms or change from baseline is > 60 ms is observed, vemurafenib may be reduced to 480 mg b.i.d.

Vemurafenib should be permanently discontinued if a QTc increase meets both criteria of > 500 ms and > 60 ms change from pre-treatment values or if QTc > 500 ms or change from baseline > 60 ms is observed on two separate prior occasions.

If a patient's study dose has been interrupted for > 4 weeks due to an AE the patient will be considered to have discontinued from the study. However, a temporary discontinuation of drug

for up to 4 weeks is allowed in case of tumour surgery or other procedures for safety reasons or in the best patient interest, or elective procedures in the best patient interest.

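### Vemurafenib is interrupted for QTc above 500 ms or a rise above 60 ms, but the only QTc condition for restarting is QTc below 500 ms, so a patient stopped for the rise alone has no recovery test to meet

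*Protocol*

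**What the plan says.** Section 6.2.1 of the protocol sets a QTc rule for vemurafenib. Section 6.3.3 sends Cohort 3b back to 6.2.1 for vemurafenib dose reductions, so the rule reaches every cohort. Its steps are:

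- **Interruption, two alternatives:** "If QTc interval exceeds 500 ms or the change from baseline is > 60 ms, vemurafenib treatment should be temporarily interrupted".
- **Checks before re-dosing:** correct electrolytes, recheck concomitant medication, and rule out or control other cardiac risk factors.
- **Restart, one criterion:** "ECG should be monitored weekly until QTc decreases to less than 500 ms, at which point treatment should be reinitiated", at one reduced dose level.
- **Second occurrence of either criterion:** the dose may be reduced to 480 mg b.i.d.
- **Permanent discontinuation:** "if a QTc increase meets both criteria of > 500 ms and > 60 ms change from pre-treatment values", or if either criterion was seen on two separate prior occasions.
- **Time limit:** a patient whose dosing is "interrupted for > 4 weeks due to an AE the patient will be considered to have discontinued from the study".

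At entry, exclusion criterion 15 (section 4.3) removes patients with a QTc at or above "450 msec at baseline or history of congenital long QT syndrome".

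**The concern.** The 60 ms criterion appears in the first interruption, the second reduction and both permanent-stop rules. It is missing only from the restart rule. For a patient stopped because of the rise, with QTc at or below 500 ms, the sentence can be read in two ways:

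- **Literally:** the restart condition and the end of weekly ECG monitoring are already met on the triggering ECG (except at exactly 500 ms).
- **As presupposing a QTc above 500 ms:** this patient has no numeric restart threshold at all.

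Either way, once the non-QTc checks are done, dosing can resume while the patient is still more than 60 ms above baseline. Section 6.2.1 adds no ECG after restart beyond the routine schedule, which widens to every 12 weeks after the first months. If an ECG is taken soon after restart, an unresolved rise could also be counted as a second occurrence, which moves the patient toward 480 mg and permanent discontinuation on the strength of one episode.

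**Working it through.** **Inputs.** Stop: QTc > 500 ms, or change > 60 ms. Restart: QTc < 500 ms. Permanent stop: both criteria together (all section 6.2.1). Baseline QTc < 450 ms (section 4.3). BRIM-2: 2 of 132 patients with QTcP above 500 ms, and "only one patient (0.8%) exhibited a QTcP change from baseline of > 60 ms" (section 1.3.5.4). Half-life about 90 hours, range 30 to 145 hours (section 1.3.3). Planned numbers: 170 for Stage I/II, maximum 490 (section 3.2).

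**Step 1: sort the states that trigger the rule.**

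| State | Condition | Consequence |
|---|---|---|
| Both criteria | QTc > 500 and change > 60 | Permanent discontinuation |
| Absolute value only | QTc > 500 and change ≤ 60 | Temporary interruption |
| Rise only | QTc ≤ 500 and change > 60 | Temporary interruption |

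**Step 2: absolute value only.** Change ≤ 60 with QTc > 500 needs baseline > 500 − 60 = 440 ms. Entry needs baseline < 450 ms. Hence baseline lies between 440 and 450 ms, and QTc is above 500 and below 450 + 60 = 510 ms. Only in this narrow band does the 500 ms test make a temporarily interrupted patient wait (apart from a rise-only stop at exactly 500 ms).

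**Step 3: rise only.** Change > 60 with QTc ≤ 500 needs baseline < 440 ms. All whole-millisecond pairs were listed, with baseline 350 to 449 ms (the lower end is assumed) and on-treatment QTc up to 600 ms. There are 4095 rise-only states. In 4005 of them QTc is already below 500 ms when the drug is stopped; the other 90 sit at exactly 500 ms. These are counts of possible states, not patient frequencies. Adding the condition of change ≤ 60 ms leaves 0 of the 4095 eligible for restart at the moment of interruption.

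**Step 4: examples.** With a baseline of 400 ms and 470 ms on treatment, the rise is 70 ms: stop, yet 470 < 500. The present rule would accept up to 499 ms, a rise of 99 ms. With the added condition the restart ceiling is 460 ms. For baselines of 380 and 420 ms the ceilings would be 440 and 480 ms.

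**Step 5: look for the condition elsewhere.** Section 5.3.8.5 only refers to 6.2.1 and 6.3.3. Section 6.3.3 has no QTc rule. Table 11 speaks of CTCAE grades without defining a QTc grade by change from baseline, and Appendix 7 gives only a link.

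**Step 6: how often.** Only one BRIM-2 patient had a rise above 60 ms, so rise-only is at most 1/132 = 0.76% (Clopper-Pearson 95% CI 0.02% to 4.15%). It is 0/132 if that patient met only the both-criteria state.

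- Rise only, at most: 170 × 1/132 = 1.3; 490 × 1/132 = 3.7.
- Either criterion, 2 to 3 of 132 depending on overlap: 170 × 2/132 = 2.6 to 170 × 3/132 = 3.9; 490 × 2/132 = 7.4 to 490 × 3/132 = 11.1.

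**Step 7: how long a stricter restart would take.** With first-order elimination, the fraction remaining after 168 h is 0.5^(168/t½): 27.4% at 90 h, 2.1% at 30 h, 44.8% at 145 h. If the rise is proportional to concentration (an assumption; section 1.3.5.4 reports only an apparent correlation), a 70 ms rise falls to 19.2 ms (1.4 to 31.4 ms) by the first weekly ECG. At 4 weeks with the longest half-life, 0.5^(672/145) = 4.0% remains.

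**The case against.** The best defence is that the rule should be read sensibly. It requires interruption, several checks, weekly ECGs and a reduced dose, so an investigator would naturally wait for a later ECG, by which time Step 7 suggests most of the rise has gone. Patients who meet both criteria are already stopped for good, recurrences lead to further reduction or discontinuation, and the investigator may withdraw anyone at any time (section 4.5). Table 11 asks for resolution to Grade 0 to 1 and does not exempt QTc; section 1.3.5.4 itself attaches a CTC grade to QTc above 500 ms. BRIM-2 also had denser ECGs than this trial, so its rate may not transfer, and its list of events possibly due to QTc prolongation contains no ventricular arrhythmia. No endpoint or error rate is affected.

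Some of this stands. Rarity, the reduced dose and the prior checks limit the severity, and the rise-only count could be zero. It does not close the gap. Expecting the investigator to wait relies on judgement the text does not require: its instruction is that treatment should resume once QTc is below 500 ms. The recurrence rules act only after re-dosing. Table 11 gives no grade for a change from baseline in the documents at hand, and a specific QTc paragraph would ordinarily take precedence over a general toxicity table. That the two can be argued against each other is a reason to say which one governs.

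**Conclusion.** The concern holds. For one of its two triggers, the QTc rule either offers a restart test that is already met at interruption or offers none, and so permits re-dosing while a stop criterion is still present. Given the entry limit and the permanent-stop rule, the 500 ms wait does real work only for baselines between 440 and 450 ms with QTc between 500 and 510 ms.

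The number affected is small: up to about 1 patient at 170 and about 4 at 490. This assumes that the BRIM-2 upper figure of 1 in 132 carries over; the 490 also assumes that all seven cohorts expand to 70. The logical gap itself rests on no assumption about rates. It should be fixed because it is a faulty safety instruction with a potentially serious consequence, not because it threatens the efficacy analysis.

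**What to change.** Amend the restart sentence in section 6.2.1 so that weekly ECGs continue, and vemurafenib is reinitiated at one reduced dose level, only when QTc is below 500 ms **and** the change from baseline is 60 ms or less. This uses the protocol's own threshold. It would also help to state that this paragraph, not Table 11, governs QTc events.

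The cost is one sentence and a few weekly ECGs of a kind the rule already calls for. The downside is that some rise-only patients will wait longer off drug and could reach the 4-week interruption limit. Under the washout assumptions above that should be uncommon, since most would qualify at the first weekly ECG.

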6.3 DOSE AND SCHEDULE OF VEMURAFENIB AND CETUXIMAB COMBINATION (COHORT 3B ONLY)

Cohort 3b has two parts;

Part 1 vemurafenib and cetuximab combination dose levels will be escalated as per [Section 6.3.1](#) sequentially in a classical 3+3 design.

Part 2 the vemurafenib and cetuximab doses will be at the recommended dose for stage I/II as determined by Part 1.

Once assigned to specific dosages of vemurafenib and cetuximab in combination, each patient will continue to be dosed at these dosages, without interruption throughout the study unless dose modification or interruption is indicated. Refer to [Section 6.3.3](#) for dose modifications guidelines for the combination of vemurafenib and cetuximab.

6.3.1 Planned Dose Escalation Levels (Cohort 3b only)

For Part 1 of Cohort 3b, the dose escalation levels of vemurafenib and cetuximab combination will be as follows:

Dose Level	vemurafenib	cetuximab
1	720 mg b.i.d. starting on Day 2 of cycle 1	Cetuximab: 300 mg/m ² loading dose and then 200 mg/m ² weekly
2	720 mg b.i.d. starting on Day 2 of cycle 1	Cetuximab: 400 mg/m ² loading dose and then 250 mg/m ² weekly
3	960 mg b.i.d. starting on Day 2 of cycle 1	Cetuximab: 400 mg/m ² loading dose and then 250 mg/m ² weekly

If the dose levels above are not tolerated then the following provisional dose levels may be considered as alternative to any of the above dose levels after discussion between the Sponsor and study Steering Committee.

Dose Level	vemurafenib	cetuximab
1A	720 mg b.i.d. starting on Day 2 of cycle 1	Cetuximab: 200 mg/m ² loading dose and then 125 mg/m ² weekly
2A	720 mg b.i.d. starting on Day 2 of cycle 1	Cetuximab: 300 mg/m ² loading dose and then 250 mg/m ² weekly

3A	960 mg b.i.d. starting on Day 2 of cycle 1	Cetuximab: 300 mg/m ² loading dose and then then 250 mg/m ² weekly
----	--	--

Patients included in Part 2 of Cohort 3b of the study will receive vemurafenib and cetuximab at the doses recommended during the dose escalation part.

6.3.2 Recommended Dose of Vemurafenib and Cetuximab

A dose will be considered non-tolerable and dose escalation will cease if 2 or more of up to 6 evaluable patients experience a DLT at a dose level. Once the non-tolerable dose is defined the MTD will be confirmed at the previous dose-level below or a dose between the MTD and the last tolerable dose (see [Section 6.3.1](#)). Six evaluable patients are required to determine the MTD.

Expected dose levels for the dose escalation are described in [Section 6.3.1](#). The dose escalation guidelines are summarized in [Section 6.3.2.1](#). Decisions to escalate or de-escalate the doses will be made based on a review of all available safety data both from the study i.e. nature of the DLTs that occurred at one dose level together with all other available data including generally available data on vemurafenib and cetuximab.

The MTD is defined to be the highest dose of vemurafenib in combination with cetuximab which can be given to 6 patients such that less than 2 subjects experience DLT within 28 days (or no more than one-third if there are more than 6 treated patients).

The recommended dose for stage I/II will be based on considerations of the estimated MTD, and on an overall assessment of safety taking into consideration tolerability data from subsequent cycles at all different dose levels tested. The recommended dose for stage I/II will be determined once the MTD is determined by the Sponsor after discussion with the study Steering Committee. The decision to continue enrolment in Cohort 3b after the Part I dose escalation phase will be decided by the Sponsor in discussion with study Steering Committee.

Dose Escalation Guidelines (Cohort 3b only)

A minimum of 3 patients initially will be enrolled at the first dose level (Dose level 1 [Section 6.3.1](#)).

The first patient entered at the first dose level will be observed for at least 28 days before the next two patients receive vemurafenib and cetuximab at that dose level. For subsequent dose levels, three patients can be entered simultaneously, although close monitoring is required.

The dose escalation rules ([Table 12](#)) proceed as follows, escalating in cohorts of 3-6 patients per dose level.

Three patients are treated at the current dose level.

- If at least 2 patients are observed to have a dose-limiting toxicity (DLT) (DLTs are defined in [Section 6.3.2.2](#)) during the 28 days following the first administration of vemurafenib and cetuximab (DLT assessment period), the MTD will have been exceeded and no further patients will be enrolled at this dose level or at any higher dose level. The prior dose level is defined as the MTD (unless only 3 patients have been treated at that level, in which case it is the tentative MTD).

- If 0 of the 3 patients are observed to have DLT during the DLT assessment period, the dose level is escalated one step for the next cohort of 3 patients, and the process continues as above.
- If exactly 1 of the 3 patients treated show DLT during the DLT assessment period, 3 additional patients are treated at the current dose level.

If none of these additional 3 patients show DLT during the DLT assessment period, the dose level is escalated for the next cohort of 3 patients, and the process continues as above; otherwise, the prior dose level is defined as the MTD (unless only 3 patients have been treated at that level, in which case it is the tentative MTD).

A tentative MTD becomes final when a total of 6 patients are treated with less than 2 showing DLT.

Once the MTD is determined, the dose to be recommended for stage I/II will be confirmed by the Sponsor in discussion with the study Steering Committee.

Table 12:
Dose Escalation Guidelines

Number of Patients with a DLT at a given dose level	Escalation Decision Guidance
0 out of 3	Enter 3 patients at the next dose level
1 out of 3	Enter at least 3 more patients at this dose level and then If 0 of these 3 patients experience a DLT, proceed to the next dose level. If 1 or more of these 3 patients experience a DLT then dose escalation is stopped and this dose is declared the maximal administered dose as the MTD has been exceeded. Three additional patients will be entered at the next lower dose level if only 3 patients were treated previously at that dose, or an intermediate lower dose level will be assessed
≥ 2	Dose escalation will be stopped. This dose level is declared the maximal administered dose (highest dose administered). Three additional patients will be entered at the next lower dose level if only 3 patients were treated previously at that dose, or an intermediate lower dose level will be assessed
≤ 1 out of 6 at highest dose level below the maximal administered dose	This is the MTD.

